3.3 Definition of Baseline values

In general, Baseline will be the last non-missing value prior to dosing. Scheduled or unscheduled measurements can be used as the Baseline value.

Measurement-specific Baseline timepoints are presented in [Table 3–1](#).

Table 3–1: Definition of Baseline

Measurement	Definition of Baseline

 Hematology, serum chemistry, urinalysis 	Baseline or if missing the Screening value

 Vital signs 	
Pre-dose for each treatment period.
 
Treatment Period 1 pre-dose Day 1 or if missing Day -1. If Day -1 is missing the Screening value will be used.
 
Treatment Period 2 pre-dose Day 12 or if missing pre-dose Day 1
 
Treatment Period 3 pre-dose Day 23 or if missing pre-dose Treatment Period 1 value
 
Otherwise baseline = day -1 pre-dose

Measurement	Definition of Baseline

 ECG 	
Time-matched predose for each treatment period.
 
Treatment Period 1 Day-1 Morning: predose, 1h, 2h, 3h, 6h similar “postdose” ; Evening: 0.5h “postdose”
 
Treatment Period 2 Day 11 Morning: predose, 1h, 2h, 3h, 6h similar “postdose” ; Evening: 0.5h “postdose”
 
Treatment Period 3a Day 22: Morning: predose, 1h, 2h, 3h, 6h similar “postdose” ; Evening: 0.5h “postdose”
 
Treatment Period 3b Day 25: Morning: predose, 1h,2h,3h, 6h similar “postdose” ; Evening: 0.5h “postdose”
 
Treatment Period 3c Day 33: Morning: predose, 1h,2h,3h, 6h similar “postdose” ; Evening: 0.5h “postdose”
 
Otherwise baseline = day -1 predose

ECG=electrocardiogram; SFU=Safety Follow-Up.

If a measurement is repeated at Baseline or a given treatment period and is obtained prior to dosing in that period, then the last available measurement will be used as the Baseline value.

12-lead ECG will be measured in triplicate with a 1-minute interval between replicates. Mean of the last three measurements predose will be taken as the baseline; if less than three replicates are available predose, the mean of the available replicates (predose) will be taken as the baseline.

Time matched predose values are defined as the Baseline value (see Table 3-1).

The change from Baseline to any subsequent post-Baseline visit will be calculated as the simple difference between that post-Baseline visit’s value and the Baseline value, as below:

$$Post - Baseline Visit Value - Baseline Visit Value$$

The percentage change from Baseline to any subsequent post-Baseline visit will be calculated as follows:

$$100 \times (Post - Baseline Visit Value - Baseline Visit Value) / (Baseline Visit Value)$$

For 12-lead ECG, time-matched differences will only be calculated for the change from Baseline.

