#### **5.2.2.2.3 Treatment Period 3c (Day 34 to Day 38)**

Study participants remain confined to the unit at the beginning of Treatment Period 3c. Study participants will receive erythromycin 500mg bid for the next 4 days (Day 34 to Day 37).

Study participants will be discharged on Day 38 at the Investigator's discretion if no serious safety issues occur.

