- o Triplicate 12-lead ECGs will be performed after a rest of at least 5 minutes at 2- to 3-minute intervals for each of the following time points: the Screening Visit; D-1; D11; D38; the EOS Visit; predose, 1h, 2h, 3h and 6h postdose for each morning dose of PSL and/or erythromycin during each treatment period; and 0.5h predose for each evening dose of PSL and/or erythromycin during each treatment period. In addition, one day prior to first dose of PSL or erythromycin in Treatment Periods 1, 2 and 3 (that is, on D-1, D10, D22 and D25), triplicate 12-lead ECGs will be performed after a rest of at least 5 minutes at 2- to 3-minute intervals for each of the following matching time points: predose, 1h, 2h, 3h and 6h postdose for the morning administration of PSL and/or erythromycin, and 0.5h predose for the evening administration of PSL and/or erythromycin, where dosing time is equivalent to the expected time of dosing on the subsequent day (the triplicate 12-lead ECG run-in day).
- p Erythromycin will not be administered on D38.
- q Blood samples (venous and MITRA) for PK analysis will be collected relative to the morning dose as follows: predose and 0.25h, 0.5h, 0.75h, 1h, 1.25h, 1.5h, 2h, 3h, 4h, 6h, 8h, and 12h postdose on D1 and D12; and predose and 0.25h, 0.5h, 0.75h, 1h, 1.25h, 1.5h, 2h, 3h, 4h, 6h, 8h, 12h, 24h, 36h, 48h, and 72h post last morning dose of PSL on D5 and D16. Additional PK trough samples will be taken immediately prior to each morning dose on D2 to D4 (Treatment Period 1) and D13 to D15 (Treatment Period 2).
- r Blood samples (venous and MITRA) for PK analysis will be collected relative to the morning dose as follows: predose and 0.25h, 0.5h, 0.75h, 1h, 1.25h, 1.5h, 2h, 3h, 4h, 6h, 8h, and 12h postdose on D26; and predose and 0.25h, 0.5h, 0.75h, 1h, 1.25h, 1.5h, 2h, 3h, 4h, 6h, 8h, 12h, 24h, 36h, 48h, 60h, 72h, 96h, and 120h post last dose of PSL on D33. Additional PK trough samples will be taken immediately prior to each morning dose on D27 to D33 (Treatment Period 3b).
- s Urine collection for PK analysis will be collected relative to the morning dose as follows:  $\leq$ 1h predose and 0h to 12h post first dose on D1 and D12; and 0h to 12h, 12h to 24h, and 24h to 48h post last PSL morning dose on D5 and D16.

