##### **8.4.2 Treatment Period 3b (Day 26 to Day 33)**

Study participants will be confined to the unit for the duration of Treatment Period 3b. Padsevonil 100mg bid will be coadministered with erythromycin 500mg bid on Day 26 to Day 32 during Treatment Period 3b. On Day 33, PSL 100mg will be coadministered with erythromycin 500mg in the morning, and only erythromycin 500mg will be administered in the evening.

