### **10.3.3 Standard 12-lead electrocardiogram**

Triplicate standard 12-lead ECGs (RR interval, PR interval, QRS interval, QT, QTcB, and QTcF) will be recorded at times specified in [Table 5-1](#), according to the following procedure: study participant lies in a supine position for  $\geq 5$  minutes; then a 12-lead ECG will be recorded in the same position. All ECG recordings will be performed in triplicate at 2- to 3-minute intervals.

Electrocardiograms will be recorded at a speed of 25mm/s and with a calibration of 1cm/mV.

The times specified in [Table 5-1](#) include a series of ‘triplicate 12-lead ECG run-in days’ to be performed 1 day prior to first PSL or erythromycin dose in Treatment Periods 1, 2, and 3 (that is, Day -1, Day 11, Day 22, and Day 25). On these days, triplicate standard 12-lead ECGs will be performed for each of the following matching time points: predose, 1h, 2h, 3h, and 6h postdose for the morning administration of PSL and/or erythromycin, and 0.5h predose for the evening administration of PSL and/or erythromycin.

By decision of the Sponsor and the Investigator, the time points specified in [Table 5-1](#) may be modified based on preliminary safety and PK assessments from previous doses tested in the study.

The Investigator or designee will determine whether the results of the ECG are normal or abnormal. All important abnormalities should be reported. The original ECG tracing will be signed or initialled, and dated by the Investigator or designee, and will be retained at the clinical site as part of the Investigator’s Site File. The original electronic file of the ECG tracing will be transferred to UCB and will remain available at least until the approval of the clinical study report.

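### SAP Table 3-1 measures the Period 3c ECG change from Day 33, a combination dosing day, so the change shows padsevonil offset and cannot show an erythromycin effect

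*SAP*

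**What the plan says.** SAP section 3.3, Table 3-1, gives each period its own time-matched ECG baseline day: Day -1 for Period 1, Day 11 for Period 2 and Day 22 for Period 3a. The last two entries are "Treatment Period 3b Day 25: Morning: predose" and "Treatment Period 3c Day 33: Morning: predose", each followed by the matching later time points.

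The dosing on those days is in the protocol. Section 8.4.2 states "On Day 33, PSL 100mg will be coadministered with erythromycin 500mg in the morning", with erythromycin again that evening. Section 5.2.2.2.3 then states "Study participants will receive erythromycin 500mg bid for the next 4 days (Day 34 to Day 37"). Day 25 is the third erythromycin-only day.

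Protocol section 10.3.3 lists the ECG run-in days ("that is, Day -1, Day 11, Day 22, and Day 25"), and a footnote to Table 5-1 lists them as "that is, on D-1, D10, D22 and D25". The lists differ on Day 10 or Day 11, but neither contains Day 33. Section 7.8.3 identifies Days -1, 11 and 22 as the run-in days without investigational product (IMP).

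SAP section 10.4.2 summarises measured ECG values and changes from the time-matched baseline with 95% CIs, and QTcF categories for observed values and for changes (cut-points 30 and 60 msec). It overlays all periods on one QTcF change plot.

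For vital signs, the same Table 3-1 uses predose Day 23, before any erythromycin, as the baseline for the whole of Treatment Period 3.

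**The concern.** Period 3c is reported as an erythromycin period, so a reader will take its change from baseline as the effect of erythromycin. The baseline day already carries erythromycin, and PSL as well. What remains after subtraction is the disappearance of PSL, with a negative sign if PSL lengthens QTcF.

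At stake is one part of the ECG safety description. Safety of PSL with and without erythromycin is a secondary objective, and ECG change is listed among the other safety variables. Protocol section 2.2 reports no clear evidence that PSL changes QTc. If that is right, the planned 3c change has expectation zero whatever erythromycin does. On the overlaid plot, a 3a curve measured from a drug-free day would sit beside a 3c curve measured from a combination day. The erythromycin effect could then appear to have vanished.

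**Working it through.** **Inputs from the documents.** Erythromycin is given on Days 23 to 37, and PSL in Period 3 on Days 26 to 33. The ECG baselines are Day 22 (3a), Day 25 (3b) and Day 33 (3c). The sample is 20 completers from up to 28 enrolled (protocol 12.7). There is no stated QTcF effect or SD, so the plan has no figure of its own to reproduce.

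**Days affected.** Erythromycin days: 37 - 23 + 1 = 15. Days 34 to 37 in 3c: 4. Share: 4/15 = 27%. Day 38 is left aside: no erythromycin is given then, and Table 3-1 does not say which baseline it takes.

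**State of the Day 33 baseline.** The 1h, 2h, 3h and 6h values follow that morning's combination dose, and the evening value precedes only the evening erythromycin dose. The morning predose value follows seven days (Days 26 to 32) of twice-daily combination dosing. All six values are therefore on-treatment.

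**Algebra.** Let E be the erythromycin effect on QTcF (stable), P the added PSL effect (additive), and r the fraction of P still present in 3c.

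| Period | Planned baseline | Planned change | Change against Day 22 |
|---|---|---|---|
| 3a | Day 22 | E | E |
| 3b | Day 25 | (E + P) - E = P | E + P |
| 3c, Days 34-37 | Day 33 | (E + rP) - (E + P) = -(1 - r)P | E + rP |

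The planned 3c change contains no E. It differs from the Day 22 change by (E + rP) + (1 - r)P = E + P, for every r.

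**Size under assumed ranges.** For E from 0 to 15 ms and P from 0 to 8 ms:
- Planned 3c change: 0 to -8 ms if r = 0; 0 to -4 ms if r = 0.5.
- Against Day 22: 0 to 15 ms if r = 0; 0 to 19 ms if r = 0.5 (15 + 0.5 × 8).

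**Effect on the ≥30 msec category.** Expected participants at one time point = n × [1 - Φ((30 - mean)/SD)], with the same SD assumed for both baselines. For 3c with P = 0 and SD 10 ms, n = 20 (n = 28 in brackets):

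| E (ms) | Planned, mean 0 | Against Day 22, mean E |
|---|---|---|
| 0 | 0.03 (0.04) | 0.03 (0.04) |
| 5 | 0.03 (0.04) | 0.12 (0.17) |
| 10 | 0.03 (0.04) | 0.46 (0.64) |
| 15 | 0.03 (0.04) | 1.34 (1.87) |

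With E = 10, P = 4, r = 0 and SD 10, the 3c means are -4 and 10 ms and the n = 20 counts 0.01 and 0.46. At ≥60 msec, for E = 15, P = 0, SD 8 to 12 and n = 20, the expected count is below 0.002 with either baseline.

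**What can be rebuilt.** With complete data and 3a tabulated separately, the mean changes chain together at each time point: (Day 25 - Day 22) + (Day 33 - Day 25) + (3c day - Day 33) = E + P - (1 - r)P = E + rP. The first two terms give the 3b mean on Day 33 against Day 22. The CIs and the participants in each change category do not chain, because they need within-participant differences. They could be recovered only from the listings.

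**The case against.** The strongest defence is that Table 3-1 follows one convention throughout: the day before each sub-period starts. ECGs at matching times are scheduled on Day 33, so no separate run-in was needed. The protocol names no ECG baseline for 3c. Period 3a already shows erythromycin against a drug-free day, the observed QTcF categories for 3c are planned, and the mean can be rebuilt. All of this is true, and it limits the consequence. It does not make the 3c change informative about erythromycin.

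Several stronger readings are tempting but not supported:

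- *The 3b baseline is also wrong, so 12 of 15 erythromycin days (80%) are affected.* Eight of those 12 days are in 3b. Day 25 is a protocol run-in day and fits the time-matched baseline of each period in protocol 12.3.2. It validly gives P, comparable with Periods 1 and 2. The lack of a 3b change from a drug-free day is a gap worth filling, not an error.
- *The SAP forbids any other contrast.* The sentence "For 12-lead ECG, time-matched differences will only be calculated for the change from Baseline" directly follows the percentage-change formula. It most naturally means that ECG gets no percentage change.
- *Day 33 is an undeclared departure from the protocol.* With no protocol-defined 3c baseline, SAP 3.9 had nothing to list as changed.
- *3a and 3c ECG changes will be averaged.* SAP 3.6 and 10 describe pooling, but section 10 defers to Table 13.1, which marks the two periods separately for ECG.
- *Participant protection is weakened.* The QTcF withdrawal criterion in protocol 6.3 names its own baseline days and does not use Table 3-1.

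**Conclusion.** The point holds for Period 3c. As written, the change on Days 34 to 37 equals -(1 - r)P and cannot show an erythromycin effect. This rests on a stable erythromycin effect and additive effects, and it concerns 4 of 15 erythromycin days. The difference from a drug-free reference is E + P. Its value is unknown, and all millisecond and count figures above rest on assumed ranges; with E = P = 0 nothing is lost.

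The consequence is a misleading descriptive output. Observed values and categories, listings and every primary PK result stand. It should be corrected because the label invites the wrong reading and the remedy is simple. For 3b, the planned analysis is sound and only incomplete.

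**What to change.** In SAP Table 3-1 and section 10.4.2:

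1. Use the time-matched Day 22 run-in as the 3c ECG baseline for changes, CIs and QTcF change categories. Drop the Day 33 change, or keep it only under the label *PSL offset*.
2. Keep Day 25 for 3b, labelled *increment of PSL over erythromycin*.
3. As an addition, summarise the 3b change and QTcF change categories against Day 22 as well.
4. State the baseline day for each curve on the overlaid QTcF plot.

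The cost is SAP wording and one further set of ECG change outputs. No new assessment is needed, because protocol section 8.3 already schedules Day 22 ECGs at the matching times. The vital signs row of Table 3-1 already takes a pre-erythromycin reference for the whole of Treatment Period 3. The drawback is that Day 22 is further in time from 3b and 3c than Days 25 and 33, so drift is less well controlled.

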3.4 Protocol deviations

Important protocol deviations (IPD) are deviations from the protocol which potentially could have a meaningful impact on study conduct or the key safety and PK outcomes for an individual subject. The criteria for identifying such protocol deviations will be defined within the protocol deviation specifications document.

Important protocol deviations will include the following categories:

- Inclusion/exclusion criteria deviations
- Administration of prohibited concomitant medications
- Deviations relating to withdrawal criteria
- Visit schedule deviations

- Study drug administration deviations (including incorrect treatment received, handling and storage deviations and incorrect dosage received) and any vomiting episode(s) (that could impact PK concentrations)
- Procedural noncompliance
- Missing data

All IPDs will be reviewed as part of the ongoing data cleaning process and data evaluation. After all data have been verified/coded/entered into a database, a data evaluation meeting (DEM) will be performed.

At least one DEM will be performed at the following time:

- Prior to the final analysis after all data have been verified/coded/entered into the database

Additional DEMs may be conducted as deemed necessary.

The purpose of these DEM reviews will be to review all protocol deviations, define the analysis sets, and check the quality of the data. The reviews will also help decide how to manage problems in the subjects' data (eg, missing values, withdrawals and protocol deviations).

Accepted deviations from scheduled time points will be described in the appropriate documents and included in the Study Master File. After the pre-analysis review, resolution of all issues, and documentation of all decisions (including inclusion into each of the analysis sets) at the final DEM, the database will be locked.

3.5 Analysis sets

3.5.1 Enrolled Set

The Enrolled Set (ES) consists of all study participants who have signed the Informed Consent form (ICF).

3.5.2 Full Analysis Set

The Full Analysis Set (FAS) consists of all study participants who have signed the ICF and received at least 1 dose of PSL. Analysis of this set will be according to the treatment the study participants actually received.

3.5.3 Pharmacokinetic-Per Protocol Set

The Pharmacokinetic-Per Protocol Set (PK-PPS) is a subset of the FAS, consisting of study participants who had no IPD affecting the PK parameters and for whom a sufficient number of samples are available to determine at least 1 PK parameter.

3.6 Treatment assignment and treatment group

All subjects will complete the identical fixed-sequence multiple-dose treatments. Listings will be presented by subject and treatment period (Screening, Treatment Periods 1, 2, 3a, 3b and 3c, and SFU). Summaries will be presented by treatment (PSL, erythromycin, PSL + erythromycin and SFU), unless stated otherwise.

- PSL Treatment Period 1 and 2 (pooled data)
- Erythromycin Treatment Period 3a and 3c (pooled data)

- PSL + Erythromycin Treatment Period 3b
- SFU

Adverse events summaries will be presented by treatment within treatment periods as follows:

- Period 1 and 2: PSL
- Period 3a: Erythromycin (pre-PSL)
- Period 3b: PSL + Erythromycin
- Period 3c: Erythromycin (post-PSL)
- SFU

PK summaries will be presented as follows:

- PSL: Period 1
- PSL: Period 2
- PSL + Erythromycin: Period 3b

3.7 Center pooling strategy

Not applicable, this is a single center study.

3.8 Coding dictionaries

Adverse events and medical history will be coded using the latest available version of the Medical Dictionary for Regulatory Activities (MedDRA[®]). Medications will be coded according to the World Health Organization Drug Dictionary (WHODD). Medical procedures will not be coded.

3.9 Changes to protocol-defined analyses

The protocol states that MITRA dried blood microsampling method will be compared to those of the plasma conventional venous sampling method using descriptive analysis (tables with summary statistics and graphs). Nonetheless, as described in [Section 9.3](#), the exploratory analysis will also be described using linear mixed effects model.

4 STATISTICAL/ANALYTICAL ISSUES

4.1 Adjustments for covariates

Not applicable.

4.2 Handling of dropouts or missing data

In general, there will be no imputation of missing data unless otherwise stated below.

Missing data will be handled as described in the sections below for safety laboratory and PK results. No other imputations will be performed.

4.2.1 Pharmacokinetics

The 95% CI lower and 95% CI upper should be left blank if the SD (or equivalently, the geometric CV) is 0. Measurements of PK concentrations that are below the limit of

quantification (BLQ) will be imputed with half of the lower limit of quantification (LLOQ) for the purpose of calculating the geometric mean and its 95% CI, the geometric CV, the arithmetic mean and SD for summaries and figures. Descriptive statistics of concentrations will be calculated if at least 2/3rd of the individual data points are quantifiable (\geq LLOQ).

For all individual PK concentration figures any concentrations that are BLQ will be regarded as missing, with the exception of predose BLQ values (linear scale only) which will be imputed as zero.

The following rules will apply for PK data listings and summaries:

- Values below the LLOQ will be reported as (BLQ) in the listings
- Descriptive statistics of plasma concentrations will be calculated if at most 1/3rd of the individual data points are missing or are not quantifiable ($<$ LLOQ) at the given time-point. Values that are BLQ will be replaced by the numerical value of the LLOQ/2 in this instance. However, if $n < 3$, then only n , minimum and maximum will be presented, and the median will also be presented if $n = 3$. The other descriptive statistics will be left blank.
- For plasma concentrations, all BLQ values occurring prior to C_{max} will be replaced by “0”, except for embedded BLQ values (between two measurable data points) which will be treated as missing. Post- C_{max} BLQ values will be treated as missing. The Pharmacokinetic analysis will be performed in accordance to the User guide for Clinical Pharmacokinetics Modeling and Simulation version 8 issued by UCB.
- For the individual figures, any concentrations that are BLQ will be regarded as missing, with the exception of predose BLQ measurements on Day 1, Day 12 and Day 23 for the treatment periods 1, 2 and 3 respectively, which will be imputed with zero for linear scale plots.
- If no subjects have data, only $n = 0$ will be presented. The other descriptive statistics will be left blank.
- The 95% CI for the geometric mean should be left blank if the SD (or equivalently, the geoCV) is 0.
- The geometric CV will be calculated using the following formula where SD is the standard deviation from the log-transformed data:

$$\text{Geometric CV (\%)} = \sqrt{[\exp(SD^2) - 1]} \times 100$$

4.2.2 Safety laboratory data

The rules for handling values that are BLQ or above the limit of quantification (ALQ) in the safety laboratory data will be the same as those described for PK data in [Section 4.2.1](#).

4.2.3 Electrocardiogram data

For the 12-lead ECG data, all calculations of changes from Baseline and descriptive statistics will be based on the mean of the triplicate assessments at each timepoint. In the event that there are not 3 available measurements at a given timepoint, the mean will be calculated based on the number of measurements for which data are provided.

4.2.4 Dates and times

Partial dates may be imputed for the following reasons:

- Classification of AEs as treatment-emergent
- Classification of medications as prior or concomitant

Imputed dates will not be shown in the listings; all dates will be displayed as reported in the database.

The following rules will be applied for partial start dates:

- If only the month and year are specified and the month and year of the first dose of study medication is not the same as the month and year of the start date then use the 1st of the month, or the date of screening if this is later (if the latter imputation results in an end date that is earlier than the start date, then use the 1st of the month). If time is missing this will be imputed as 00:00 h
- If only the month and year are specified and the month and year of the first dose of study medication is the same as the month and year of the start date, then the date of the first dose of study medication will be used. If this results in an imputed start date that is after the specified end date, then use the 1st of the month, or the date of screening if this is later (if the latter imputation results in an end date that is earlier than the start date, then use the 1st of the month). If the imputed date is the date of dosing then time will be imputed as the start time of the dosing (ie, event will be regarded as treatment-emergent)
- If only the year is specified, and the year of the first dose of study medication is not the same as the year of the start date then January 01 will be used. If time is missing this will be imputed as 00:00 h
- If only the year is specified, and the year of the first dose of study medication is the same as the year of the start date, then the date of the first dose of study medication will be used. If this results in an imputed start date that is after the specified end date, then January 01, or the date of screening if this is later will be used (if the latter imputation results in an end date that is earlier than the start date, then January 01 will be used). If the imputed date is the date of first dose of study medication then time will be imputed as the start time of the study medication intake (ie, event will be regarded as treatment-emergent)

The following rules will be applied to partial stop dates:

- If only the month and year are specified, then use the last day of the month
- If only the year is specified, then use December 31 of the known year
- If the stop date is completely unknown, do not impute the stop date

Missing or partially missing dates and/or times will be imputed as described in [Table 4-1](#) for the calculation of duration of each AE. Adverse event duration is computed in and reported in day and time format: xx d hh:mm.

Table 4-1: Calculation rules for duration of adverse events			
Data availability	Onset date/time	Outcome date/time	Calculation rules
Complete data	D1/T1	D2/T2	Duration = [(D2 – D1)*24 + (T2 – T1)]/24 d

Table 4-1: Calculation rules for duration of adverse events			
Data availability	Onset date/time	Outcome date/time	Calculation rules
End time missing	D1/T1	D2/--	End time is substituted by time 23:59h (=23.98 in decimal format) Duration = $\langle [(D2 - D1) * 24 + (23.98 - T1)] / 24 \text{ d}$
Start time missing	D1/--	D2/T2	Onset time is substituted by time 00:00h Duration = $\langle [(D2 - D1) * 24 + T2] / 24 \text{ d}$
Start and end time missing	D1/--	D2/--	Duration = $\langle D2 - D1 + 1$
Start day and time missing	--/--	D2/T2	Duration = $\langle [(D2 - D0) * 24 + (T2 - T0)] / 24 \text{ d}$ For a subject in the FAS, D0 and T0 are the date and time of first administration of study medication and for screen failures, D0 is the date of the screening visit and T0 = 00:00h
End day and time missing	D1/T1	--/--	If the stop date is missing, duration will not be calculated.
Start and end date missing	--/--	--/--	If the stop date is missing, duration will not be calculated.

FAS=full analysis set; PSL=Padsevonil.

